MyVoice is a web-based patient-centered decision aid developed to help women with rheumatic diseases make informed decisions about pregnancy and other family planning decisions. This pilot trial is designed to assess the extent to which MyVoice decision aid can be feasibly and acceptably implemented into the rheumatology clinical setting and will inform operational procedures for a future hybrid effectiveness-implementation trial. Women in the intervention arm will receive the MyVoice decision aid (n=38). Women in the control arm (n=12) will receive a paper-based version of the American College of Rheumatology pamphlet about pregnancy, which, similarly to MyVoice, targets women with a broad range of rheumatic diseases.

[figure not shown]
B. Protocol Summary

| | |
|---|---|
| Title: | A Pilot Study to Assess Feasibility and Acceptability of MyVoice, a Family Planning Decision Aid for Women with Rheumatic Diseases |
| Grant Number: | K23 AR075057-01A1 |
| Study Description: | This protocol describes procedures and goals for the pilot testing of MyVoice, a web-based decision aid to help women with autoimmune diseases clarify their reproductive goals and learn about if and how their autoimmune diseases and medications affect these goals. Primary hypothesis: MyVoice will be feasible and acceptable to patients who receive rheumatology care. |
| Objectives* : | Our aim is to conduct a pilot trial to assess feasibility and acceptability of MyVoice vs. a patient pamphlet among female patients ages 18-44 (n=55) who receive rheumatology care. |
| Endpoints* : | Feasibility measures: 
-Number of women who express interest in the study vs who are contacted-Number of women who enroll vs. decline to participate-Completion rates for MyVoice-Technical feasibility (e.g., software reliability of MyVoice)-Number of consented women who complete the study vs. number of consented women who partially complete the study or do not open or utilize the study materials Acceptability measures: 
-Completion rates for MyVoice-Patients' satisfaction with MyVoice or pamphlet-Patients' comprehension of instructions, scales, and surveys-Completion rates for instructions, scales, and surveys Preliminary implementation measures: 
-Surveys of barriers/facilitators of use-Survey of physicians' readiness to adopt the intervention in clinic-Technical issues with video visits/Epic-Number of patients who no-show for their telemedicine visits |
| Study Population: | We will recruit 55 women aged 18-44 who are diagnosed with rheumatoid arthritis, myositis, systemic sclerosis, or systemic lupus erythematosus who receive care at one of three UPMC rheumatology clinics. Participants cannot be pregnant and cannot be sterilized. |
| Phase* or Stage: | Phase II |
| Description of Sites/Facilities Enrolling Participants: | Participants will be recruited from the UPMC Falk Rheumatology Clinic, the Lupus Center of Excellence, and the Magee Women's Health Rheumatology Clinic. |
| Description of Study Intervention/Experimental Manipulation: | Interested individuals will arrive at the clinic one hour prior to their scheduled rheumatology appointment. They will be consented and randomized to either receive the intervention (the MyVoice decision aid, an interactive website) or to receive the control pamphlet. They will have approximately 40 minutes to review the tool or pamphlet prior to meeting with their rheumatologist. |

Study Duration* : Nine months

Participant Duration: Two hours.

C. Study Flow Chart and Randomization Schema

Below is a detailed description of the data in each survey [Appendix] collected at each time point.

T0: Baseline Survey

- National Survey of Family Growth Family Planning Services Question
- COLLABORATE shared decision-making scale
- Self-efficacy (Perceived Efficacy in Patient-Provider Interactions [PEPPI])
- Reproductive knowledge (ReproKnow)
- Desire to avoid pregnancy scale (DAP)
- Demographic questionnaire

T2: Exit Survey

- Acceptability and implementation measures for the MyVoice tool
- Reproductive knowledge (ReproKnow)
- Self-efficacy (Perceived Efficacy in Patient-Provider Interactions [PEPPI])
- Decision Conflict Scale (Low Literacy version)
- Interpersonal Quality of Family Planning (IQFP) Scale

T3: Provider Survey

- Providers' experiences with the study as well as information related to encounters with patients enrolled in the study

T4: 3 Month Survey

- National Survey of Family Growth Family Planning Services Question
- Self-efficacy (Perceived Efficacy in Patient-Provider Interactions [PEPPI])
- Reproductive knowledge (ReproKnow)
- London Measure of Unintended Pregnancy

D. Risk/Benefit Assessment

Known Potential Risks

- Discomfort- Study activities involve information regarding reproductive health; some individuals may be uncomfortable discussing this topic.
- Invasion of Privacy- Participants may feel uncomfortable discussing their reproductive health where other individuals may hear them.
- Breach of Confidentiality- Any possibility that de-identified information could be viewed by unauthorized parties.

Known Potential Benefits

- This pilot study will inform the procedures and practices related to a future full-scale testing of a patient-facing decision support tool for family planning. Our study team and others have demonstrated that women with rheumatic diseases do not receive adequate family planning care. We will not directly counsel patients about their particular risks, and therefore, patients will not receive a direct benefit from their participation. However, they may learn more about their family planning options in the context of their diseases.

Assessment of Potential Risks and Benefits

- Discomfort- We will minimize occurrence of discomfort by being clear about the content of the study tool and assessment measures during recruitment. All questions in study surveys and interviews will be optional, and participants will be told they can skip any question they do not wish to answer.
- Invasion of Privacy- The study will not be discussed with potential or current participants in public settings. Conversations about the study will only occur in private exam rooms or research spaces or via email or phone conversations. We will minimize risk by placing phone calls while in a private room and asking the potential participant whether they are in a private location before discussing the study.
- Multiple steps will be taken to prevent any breaches in confidentiality, including not recording patients' names or linking their names to their assessments. All study data collected from the participants will be assigned a numerical code in order to de-identify it and minimize the risk of a breach of confidentiality. will minimize the severity of the potential risks by not asking for highly personal or sensitive information in the assessment or demographic survey.
- Every step will be taken to avoid or minimize the above risks. Because this is a minimal risk study, we feel the potential benefits of the study outweigh the outlined risks. We will remind participants that they can withdraw from the study at any time.

E. Screening Procedures

C1. Eligibility Criteria

C1a. Inclusion Criteria

Participants are eligible to participate if they meet the following criteria:

- Diagnosed with at least one of four rheumatic diseases diagnosed by a rheumatologist: rheumatoid arthritis (RA), systemic sclerosis (SSc), myositis, and systemic lupus erythematosus (SLE).
- Enrolled in a disease registry for RA, SSc, myositis, or SLE
- Female sex assigned at birth
- Age 18-44 (reproductive age as described by the Centers for Disease Control and Prevention)
- Able to read and speak English
- Access to a smartphone, personal computer, or tablet

Rheumatology providers are eligible to participate if they meet the following criteria:

- Rheumatologist who sees patients in the UPMC system

C1b. Exclusion Criteria

Participants are ineligible to participate if they meet any of the following criteria:

- Prior hysterectomy or sterilization
- Currently pregnant
- Do not have access to a smartphone, personal computer, or laptop
- Do not see a rheumatologist in the UPMC system

F. Recruitment Plan

Due to the current COVID-19 pandemic, we anticipate that some potential participants will be completing their medical visits remotely via video with their rheumatologists. To ensure that all eligible potential participants are given equal access to our study and to reduce potential bias in only recruiting participants who are willing or able to come to the rheumatology clinic in person, we will offer both remote (telemedicine) and in-person (clinic) study participation and will recruit both remotely and in clinic.

Although enrollment, randomization, and all non-exploratory outcome measures are occurring in one day, we anticipate some possibility of attrition. Therefore we will recruit a maximum of 55 participants with the goal of 50 participants completing the aforementioned activities. This is a pilot study; therefore, outcomes are primarily related to feasibility and acceptability. Furthermore, we have no sample size calculations in this proposal for which we need to account for participant attrition.

D1. Recruitment Tracking

This section describes the protocol for tracking potential participants through the recruitment process.

All recruitment documentation and tracking will take place in the “Recruitment Tracking” spreadsheet in SharePoint. After screening for eligibility in the clinic schedules, research coordinators will enter all patient information into the “Approaching in Clinic” tab. The following information will be documented:

- Name
- Appointment Date
- Appointment Time
- Provider
- Age
- Disease diagnosis

Research coordinators will enter potential registry participants into the “Registry Enrollees” tab of the spreadsheet with the same information entered.

Research coordinators will enter potential participants into the recruitment spreadsheet in the “Interested” tab immediately upon expressing interest in study participation. The following information will be documented in SharePoint:

- Name
- Phone Number
- Email Address
- Mode of Contact (in person, text, email, phone)
- Date of Interest

If any information is missing or not given by a potential participant, research coordinators will leave it blank.

This interest can be expressed in person or remotely via phone, email, or text.

All participants will then be assigned a recruitment status which can be updated at any time to reflect changes in status.

Explanation and instructions for categorization of Participant Recruitment Status:

- Interested: patient has expressed interest in participating, screening not yet completed
 - If and when screening is complete, patient will be moved to appropriate recruitment status as described below
- Maximum attempts reached: study staff has reached out to interested patient three times without a response
 - Study staff will not contact interested patients again unless contacted by patient
- Ineligible: patient is ineligible to participate based on screening criteria
 - Study staff will not assign patient an ID in REDCap
- Enrolled: patient is interested in participating and decides to enroll
 - Study staff will assign patient an ID in REDCap

D2. Remote Recruitment

Existing patients who have scheduled video return visits with their rheumatologists:

Research coordinators will identify registry patients who appear to meet inclusion/exclusion criteria and have upcoming telemedicine rheumatology visits within 12 weeks. There are currently 303 eligible patients already identified within the existing rheumatology research registries (listed below) willing to be contacted for future studies.

Registries:

1. UPMC Lupus Center of Excellence Patient Registry (STUDY19060329)
2. Rheumatoid Arthritis Comparative Effectiveness Research (RACER) registry (STUDY19090282)
3. Banking of Biological Samples and Collection of Clinical Data for Connective Tissue Disease Research (STUDY19090054)

We will start recruitment with these patients. All patients who are able to conduct video visits for UPMC are assumed to have access to smartphones or tablets/laptops/PCs.

Patients will be contacted via phone, email, or by mail to inquire if they would be amenable to discussing our study with a research coordinator. Patients who are amenable will contact one of the research coordinators, [name] or [name], at their office phone numbers (voice mail checked daily) or via email. Research coordinators will discuss the study with patients prior to their rheumatology visits, and screen for eligibility and interest. The coordinator will also provide a link for the written informed consent form, which patients can review while she is on the phone call with them or at a later time. They will be asked to sign the form electronically if they consent to participation. If they desire more time to think about the study and review the consent document before committing, they will be given the research coordinator's information to contact her if they wish to enroll in the study. Verbal consent may also be provided to patients based on their preference or ability to electronically sign a consent document. Participants will also sign a HIPAA authorization allowing study personnel to access their medical records. This form will be discussed over the phone, and an electronic version will be sent via DocuSign to the participant's email. DocuSign will send out automated reminder emails to participants to remind them to complete the consent form. Once completed, DocuSign automatically uploads the completed document to the DocuSign site and notifies the research study staff of form completion.

D3. Clinic Recruitment

Recruitment will occur among patients who receive care at three UPMC rheumatology clinics that are located within a three-mile radius of each other:

UPMC Falk Clinic

[name]
[name]
[name]
[contact]

UPMC Mercy

[name]
[name]
[name]
[contact]

Lupus Center of Excellence

[name]
[name]
[name]
[contact]

Research coordinators will identify registry patients who have upcoming in-person clinic visits within 12 weeks, screen for eligibility and interest as above, and ask them to come to their next clinic visits one hour early to provide consent and engage in study procedures. They will also sign a HIPAA authorization allowing study personnel to access their medical records.

D4. Provider Recruitment

Rheumatologists within the UPMC healthcare system will be notified via email when the study begins recruitment. Drafted language for recruitment notification sent to rheumatology providers (distributed by [name]):

“Dear Colleagues,

I am principal investigator of a research study that is testing the benefit of a web-based family planning decision aid for women with rheumatic diseases that will begin soon. The study will be recruiting. The purpose of this email is simply informational—no action is required on your part. Women enrolled in the study who use the decision aid will get a printout summary sheet generated by the decision aid and some patients may wish to share this with you, their care providers. Please treat this summary sheet similarly to any other information patients bring to their appointments. Please feel free to reach out if any questions or concerns arise.”

Note: Edits to this language should include only site-specific changes to the clinic name.

Rheumatology providers with enrolled patients will be asked to complete a survey at T3 (described in study procedures section). The registry database indicates the rheumatologist that the patient sees, which will be confirmed using Epic Hyperspace. If one or more of their patients completed the study, rheumatologists will be encouraged, via email, to complete an anonymous REDCap survey about their experiences with the study and related patient encounters. This will occur 2 weeks after the final patient participant completes the study. Rheumatologists will not be informed by study personnel which of their patients participated in the study.

D5. Additional Recruitment Methods

D5a. Pitt+Me

We do not anticipate difficulty recruiting 55 women using our remote and in clinic recruitment methods. However, if we are not recruiting 2-3 patients per week after 2 months, we will begin recruitment with Pitt+Me.

A description of the study will be posted on CTSI’s Pitt+Me research registry website for women to self-refer. Pitt+Me also distributes emails that will advertise the study to women who may be

eligible based upon demographics and/or participant-chosen health areas of interest. Pitt+Me advertises over multiple social media avenues such as Twitter and Facebook.

Because our remote and in clinic recruitment stems from a registry of UPMC rheumatology patients and EPIC schedules for rheumatology providers within UPMC, we will need to confirm that all interested patients referred through Pitt+Me meet the same criteria as those recruited remotely or in clinic. Pitt+Me patients must therefore be screened to ensure that they meet the following inclusion criteria:

- Under the current care of a UPMC rheumatologist
- An upcoming scheduled appointment with their UPMC rheumatologist within the next 3-4 months

To confirm patient answers to the prescreening questions and to confirm eligibility, research coordinators will ask for verbal approval to access the patient's EPIC medical records. Patients will be reassured that their medical information will remain confidential and will not be used for anything other than to confirm eligibility. If verbal approval is given, coordinators will then check the patient's medical records to confirm the patient's responses. If the patient is eligible, they will be further screened based on inclusion criteria described in the Screening Procedures section. If the patient is found to be ineligible after the prescreen, she will be informed that she cannot complete the study.

G. Materials List

The following is a list of items that need to be brought to the clinics with research staff for in-person study visits:

- Paper printouts of baseline and exit surveys
- Stylus
- iPad
- iPad charger
- iPad keyboard
- Disinfecting wipes
- Audio recorder
- Audio recorder batteries (AAA)
- Pens
- Smartphone with voice recording technology (for backup)
- Vincent payment cards
- Vincent payment brochures
- Ear plugs
- REINA Registry consent forms

All materials will be located in a study kit for easy transport to and from clinic visits. At least two study kits will be made available to allow for both research coordinators to complete study visits simultaneously, if needed.

H. Data Collection and Entry

F1. REDCap Instructions

Accessing REDCap Database

Pitt Log in Page <https://www.ctsiredcap.pitt.edu/redcap/>

REDCap Account Request Form (Pitt)

<https://www.ctsiredcap.pitt.edu/redcap/surveys/?s=injPIG>

REDCap Introductory/Training Videos – general overview information of how to use REDCap

- <https://projectredcap.org/resources/videos/>
- <https://redcapinfo.ucdenver.edu/redcap-videos.html>

F1a. Form Completion Instructions

To enter participant data:

- Click “Add/Edit Records”
- For a participant with an existing ID, choose appropriate participant ID from the drop down menu
- For a new participant without an existing ID, click “Add new record”
- Choose appropriate form corresponding to the time point of the participant to enter data or administer survey

F1b. Order of Form Completion

- Time point T0: MyVoice RD Baseline Survey
- Time point T2: MyVoice RD Exit Survey
- Time point T3: MyVoice RD Provider Survey
- Time point T4: MyVoice RD 3 Month Survey
- Withdrawal Form: MyVoice RD Withdrawal Form

Throughout time points T0-T4 (delineated in “Study Procedures”), participants will be asked to complete a series of surveys to gather study information. Clinic patients will complete all surveys on an iPad provided by the research team. Telemedicine participants will be required to complete all surveys on their own smartphone, personal computer, or tablet. All surveys are located in REDCap within the “MyVoice RD Pilot” study page.

F2. Telemedicine Participants

To access study forms and surveys for telemedicine participants, research coordinators must send a REDCap link to participants via email as described in the REDCap Instructions section. Study participants will then enter their own data using the REDCap link. During the remote study visit, research coordinators will call the participant on the phone to assist with any issues or to answer any questions that participants may have and will remain on the phone until study activities are completed.

F3. Clinic Participants

To access study forms and surveys for clinic participants, research coordinators must log in to their REDCap account to administer the surveys. During the in-person clinic study visit, research coordinators will log in to their REDCap accounts, open the appropriate surveys for each specific time point, and administer the survey to participants by allowing participants access to the iPad to answer the questions confidentially. Coordinators will be present for the duration of the survey completion to assist with any iPad issues or to answer any questions that participants may have.

F4. Troubleshooting

F4a. REDCap Issues

Should there be an unforeseeable issue with REDCap during a telemedicine or clinic study visit that prevents REDCap log in, research coordinators will be prepared with paper copies of all study forms and surveys located in their study kits.

For telemedicine participants, research coordinators will administer all surveys over the phone to participants and record their responses on a paper form. For clinic participants, research coordinators will allow participants to complete paper copies of the surveys themselves. Once REDCap is accessible again, the coordinator who administered the surveys will then record participant responses in REDCap manually and retain all paper copies.

If REDCap experiences issues while participants are logged in and completing surveys, the research coordinator will contact the REDCap support administrator at [Pitt Biomedical Informatics [contact]](mailto:[contact]) to attempt to restore any survey responses already recorded. If REDCap is still experiencing issues, the study will continue with paper form protocol as described above.

F4b. Internet Connection Issues

Should telemedicine participants experience an issue with their own internet connectivity/WiFi that prevents them from logging in to REDCap, the research coordinator will administer the surveys over the phone while logged in to REDCap and will enter all responses in real time.

For clinic participants, any issues with internet connectivity/WiFi within the clinics will follow paper form protocol by having participants complete the surveys on a paper copy of the surveys. Once access to an internet connection/WiFi is regained, the coordinator who administered the surveys will then record participant responses in REDCap manually and retain all paper copies.

I. Study Procedures

After eligible participants are screened and enrolled, participation in the study can begin. While it is preferred that participants answer as many questions on the surveys and complete as much of the study activities as they can, participants will be reminded that all questions and activities throughout the study are completely voluntary, and they do not need to answer any questions they do not wish to answer. In this case, there is a “prefer not to answer” response for all survey questions.

G1. Randomization

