This study will comply with the NIH Data Sharing Policy and Policy on the Dissemination of NIH-Funded Clinical Trial Information and the Clinical Trials Registration and Results Information Submission rule. As such, this trial will be registered at ClinicalTrials.gov, and results information from this trial will be submitted to ClinicalTrials.gov. In addition, every attempt will be made to publish results in peer-reviewed journals. Data from this study may be requested from other researchers one year after the completion of the primary endpoint by contacting [name] [name]. Only de-identified data will be shared and will not be traceable back to individual participants.

M. Appendix

Screening Script

Hi Ms (_____),

Thank you again for participating in the Pitt (disease) registry. We have a new research study we wanted to tell you about. This research study is being conducted by University of Pittsburgh Division of Rheumatology and is funded by a grant from the National Institutes of Health.

The purpose of the research study is to explore whether a web-based tool called MyVoice or a pamphlet from the American College of Rheumatology helps women with autoimmune diseases to get the information and support they need to make informed decisions about if and when to have a child, and gives them information about birth control, fertility options, and how their diseases and medications might affect a pregnancy.

Does this sound like it might be of interest to you?

If No, thank the patient and hang up.

If Yes, continue

Let me tell you a little more about the research study to help you to make up your mind.

This research study will be conducted remotely. You'd need to have access to the Internet to complete this study.

Do you have access to Internet? (probe: smart phone, laptop, personal computer, tablet, etc)

If No, thank the patient and hang up.

If Yes, continue

Great. Two weeks before your next appointment with your rheumatologist, we would email or text you a link with some surveys to complete, along with either the web-based tool or a link to the pamphlet from the American College of Rheumatology. We will send you some email or text reminders to complete the study.

Overall, we think the surveys will take about 30 or 40 minutes to complete, and the tool will take about 20 minutes or so to navigate through.

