[Prompt] Were those conversations different at all after using MyVoice:RD?

- Do you feel confident in your ability to get answers to your reproductive health question? Seek out reproductive health care?

[Prompt] Did MyVoice:RD help at all?

N. Statistical Analysis Plan

Measures

We collected baseline information about participants' demographic and personal characteristics. Questions about contraception use, reproductive histories, and healthcare utilization were adapted from the National Survey of Growth. The Desire to Avoid Pregnancy scale was used to assess patients' preferences around a future pregnancy.

Feasibility, usability, and acceptability of MyVoice:Rheum and the control pamphlet were assessed using qualitative and quantitative measures. The validated Intervention Appropriateness Measure (IAM) and Acceptability of Intervention Measure (AIM) consist of Likert scales ranging from 1-5; we assigned a feasibility threshold of ≥ 3.5 of 5 for AIM and IAM scores, for which higher scores indicate more positive responses. Usability was assessed via summary scores from the System Usability Scale (SUS), which consists of a 10-item Likert scale with scores ranging from 0-100; we set a threshold of scores >80.3 as 'A'/excellent and 68-80.3 as 'B'/very good, consistent with standard rating for the SUS. To assess the perceived value of MyVoice:Rheum and the pamphlet, we developed a five-item Likert scale with responses ranging from 1-5 (1: strongly disagree, 5: strongly agree).

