facilitate coding and thematic analysis. Transcripts were reviewed by two experienced qualitative analysts with master's degrees in public health and sociology, respectively ([name], [name]). [name] and [name] used an open coding approach to identify themes that arose inductively, and subsequently refined the codebook based on the most frequent and important codes. [name], a trained research assistant, also independently coded the transcripts. As a form of investigator triangulation, the analysts and P.I. ([name]) used a consensus approach to reconcile coding and create new codes. Focus coding was used to re-review all transcripts and synthesize themes.

RESULTS

Sample Characteristics

Fifty-five patients consented to participate in the study, among whom 46 patients were randomized to a study arm. Forty patients completed the study, among whom 31 patients were randomized to the MyVoice:Rheum intervention and 9 were randomized to the control arm. The most common rheumatic disease diagnoses were SLE, RA, and myositis. Most participants identified as heterosexual, and nearly half of all participants were married. More than half of participants had at least a college degree. Over 40% of participants identified their rheumatologist as their main health provider. Most participants had never been pregnant, and approximately 10% had a diagnosis of infertility. Over two-thirds of participants used a method of contraception.

Quantitative Outcomes

MyVoice:Rheum and the control pamphlet were both rated as feasible, acceptable, usable, and valuable by study participants. The minimum threshold score of 3.5 for the Acceptability of Intervention Measure (AIM) was met or exceeded by 96.8% of MyVoice:Rheum users and 88.9% of controls; average AIM scores for MyVoice:Rheum and controls were 4.4 (S.D. 0.58) and 3.97 (S.D. 0.65), respectively. The minimum threshold score of 3.5 for the Intervention Appropriateness Measure (IAM) was met or exceeded by 96.8% of MyVoice:Rheum users and 88.% of controls; average IAM scores among MyVoice:Rheum and controls were 4.48 (S.D. 0.60) and 4.11 (S.D. 0.85), respectively. System Usability Scale scores for MyVoice:Rheum users were rated in the range of "excellent", whereas scores for pamphlet users were rated in the range of "very good" (83.0 vs. 79.3, respectively).

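### No result is defined in advance that would refute the primary hypothesis of feasible and acceptable, and the feasibility verdict rests on completers' ratings rather than on the protocol's listed feasibility measures

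*Combined protocol and SAP*

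**What the plan says.** The Study Description in Section B (Protocol Summary) states: "Primary hypothesis: MyVoice will be feasible and acceptable to patients who receive rheumatology care". The Endpoints row of the same table lists five feasibility measures, for example "Number of women who enroll vs. decline to participate", and four acceptability measures, for example "Patients' satisfaction with MyVoice or pamphlet". MyVoice completion appears in both lists. No measure is marked as leading and none carries a success mark. Section L (Publication and Data Sharing Policy) refers to data requests "one year after the completion of the primary endpoint", but no section says what that endpoint is.

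The protocol body describes the exit-survey content only as "Acceptability and implementation measures for the MyVoice tool". In the supplied text the scales are first named in Section N (Statistical Analysis Plan), under Measures, which is in the past tense and is followed by results. There, "we assigned a feasibility threshold of ≥ 3.5 of 5 for AIM and IAM scores". SUS scores above 80.3 are graded excellent and those from 68 to 80.3 very good. The five-item value scale has no mark. Under Analysis, feasibility and acceptability are to be described, not tested.

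The Quantitative Outcomes text concludes: "MyVoice:Rheum and the control pamphlet were both rated as feasible, acceptable, usable, and valuable by study participants".

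**The concern.** A primary hypothesis needs some result that would count against it. Here three things are left open: which measure decides, whether 3.5 is a mark for the average or for the individual woman, and how many women must reach it. SUS has grades but no named passing grade.

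The feasibility half is the weaker one. The 3.5 mark is called a feasibility threshold but is applied to scales of acceptability and appropriateness. The listed feasibility measures, which concern interest, enrolment, completion and software reliability, play no visible part in the conclusion. The pilot exists to inform the procedures of a larger trial. A reader planning that trial could take the word feasible to mean that recruitment and completion met a standard, when no standard was set and those results were not judged.

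**Working it through.** **Inputs.** All come from Section N, Results, unless noted: 55 consented, 46 randomised, 40 completed (31 MyVoice, 9 control). AIM at or above 3.5: 96.8% of MyVoice users and 88.9% of controls. Mean AIM (SD): 4.4 (0.58) and 3.97 (0.65). From Section F (Recruitment Plan): "Therefore we will recruit a maximum of 55 participants with the goal of 50 participants completing the aforementioned activities".

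**Step 1: reproduce the printed percentages.** 30/31 = 96.8% and 8/9 = 88.9%. The denominators equal the completers in each arm. No other denominator fits. At least 31 MyVoice and 9 control women were randomised, so the arms can have held at most 46 − 9 = 37 and 46 − 31 = 15. The nearest alternatives, 29/30 = 96.7% and 31/32 = 96.9%, do not match. The counts are inferred, since only percentages are printed.

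**Step 2: exact 95% intervals** (Clopper-Pearson: lower limit = Beta quantile 0.025 with parameters x, n−x+1; upper limit = Beta quantile 0.975 with parameters x+1, n−x).

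| Quantity | x/n | % | 95% CI |
|---|---|---|---|
| AIM ≥ 3.5, MyVoice completers | 30/31 | 96.8 | 83.3 to 99.9 |
| AIM ≥ 3.5, control completers | 8/9 | 88.9 | 51.8 to 99.7 |
| Completed, of consented | 40/55 | 72.7 | 59.0 to 83.9 |
| Completed, of randomised | 40/46 | 87.0 | 73.7 to 95.1 |

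The completion goal is 50/55 = 90.9%. It lies above the interval for consented women and inside the interval for randomised women. The endpoint list names consented women as the denominator; nine of them (55 − 46) were never randomised.

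**Step 3: set the listed feasibility measures beside the results text.**

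- Interest against number contacted: not reported.
- Enrolment against refusal: number declining not reported.
- MyVoice completion: not reported, and not derivable because the number randomised to each arm is not given.
- Software reliability: not reported.
- Completion among consented women: counts given, not judged.

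The verdict also says valuable, but no value-scale figure is printed in the results text.

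**Step 4: does the unit of the 3.5 mark matter?** For the MyVoice data in hand, hardly. The mean is 4.4 (95% CI 4.4 ± 2.04 × 0.58/√31 = 4.19 to 4.61), and any required share up to 96.8% is met. As a rule fixed beforehand it would matter a good deal. Suppose, for illustration, normal scores with SD 0.58, n = 31 and a true mean of 3.8; about 70% of women would then reach 3.5. A rule that the mean be at least 3.5 passes with probability 0.998. A rule that at least 80% of women (25 of 31) reach 3.5 passes with probability 0.13.

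**The case against.** The best defence is that this is a descriptive pilot. The introduction speaks of the extent to which MyVoice can be implemented and of informing procedures. No go/no-go decision is described, there is no sample size calculation, and Section N says pilots are not built for hypothesis testing. Section N also says that feasibility was assessed qualitatively as well, and one interview theme reports that users found MyVoice feasible. It follows that no significance test is needed and that insisting on a single lead endpoint would be partly a matter of taste. But the remark about hypothesis testing introduces the comparison of family planning discussions between arms, and it does not withdraw the primary hypothesis. A theme from interviews with users does not say what finding would have been negative, nor does it replace the listed counts.

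Several stronger readings are tempting, and the documents do not support them.

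- A reader might infer that the hypothesis could not fail. A mean or an individual score could miss 3.5, and a SUS score could fall below 68. What is missing is the rule that turns such a miss into a conclusion.
- A reader might infer that the scales and marks were chosen after the data were seen. The past tense shows when Section N was written, not when the marks were set. The survey forms, cited as an appendix, are not in the supplied text and may name the scales.
- A reader might infer that 40 of 55 means the pilot failed its own criterion. The 50-of-55 figure is an attrition allowance covering both arms and is not called a success criterion. Nor is it the only numeric target: Section F also sets 2-3 recruits per week as the trigger for adding a recruitment source.
- A reader might infer from the shared verdict that the measures do not separate the arms. The hypothesis concerns MyVoice alone, and the SUS grades differ (83.0 excellent, 79.3 very good).

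**Conclusion.** The point stands in limited form. The primary hypothesis is stated without a deciding measure, without a unit or required share for the one mark given, and without any result defined as refuting it. The acceptability finding for MyVoice is favourable among completers whichever way 3.5 is read. The feasibility finding is not supported as written: it rests on completers' ratings, four of the five listed feasibility measures are not reported in the results text, and the fifth (72.7% of consented women, 87.0% of randomised women) is left unjudged. For the pamphlet, nine women give an interval of 51.8 to 99.7%.

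This assumes that the counts inferred from the percentages are right and that completing the study in the results means the same as in the Section F goal. A reader might also want to test stricter marks than 3.5. The documents propose none, and a normal curve with mean 4.4 and SD 0.58 puts about 15% of scores above the scale maximum of 5, so modelling of that kind is not reliable here.

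This is a reporting improvement worth making, not a flaw that invalidates the pilot.

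**What to change.** - In Section N, Measures, state that the 3.5 and SUS marks are not in the protocol's endpoint list and, unless a dated record shows otherwise, were not pre-specified.
- In Section N, Results, replace the four-part verdict with estimates and intervals for every measure in the Section B endpoint list and for the rating scales. Include the four rows tabulated above, with counts confirmed from the data, and show completion beside the goal of 50 from a maximum of 55.
- Describe the rating-scale results as acceptability, appropriateness and usability among completers, and rest any feasibility statement on the listed feasibility measures.
- Do not fix a lead measure or required share now as though it had been planned, because 96.8% is already printed. Set it for the future trial, or label it post hoc here.

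The cost is wording and a few tabulations of data that should already exist, with no new participants. The downside is a less favourable and more qualified headline.
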